6.14 Follow-up

All subjects discontinued from protocol-prescribed therapy for any reason will be followed for a period of 28 days following the last dose of IP or until the date of the last study visit, whichever is later, for the collection of AEs, concomitant medications, therapies and procedures, transfusions administered and healthcare resource utilization. Females of childbearing potential should avoid becoming pregnant for 3 months after the last dose of IP and male subjects should avoid fathering a child for 3 months after the last dose of IP.

All subjects discontinued from protocol-prescribed therapy for any reason will also be followed for survival, subsequent MDS therapies, progression to AML and second primary malignancy every month for the first year following Treatment Discontinuation and every three months thereafter until death, lost to follow-up, or withdrawal of consent for further data collection. The investigator must make every effort to obtain information regarding the subject's survival status before determining the subject is lost to follow-up. Survival follow-up can be performed via the telephone.

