10.6.2 Secondary Efficacy Analyses

10.6.2.1 Key Secondary Efficacy Analyses

Overall survival (OS), defined as the time from randomization to death from any cause, will be calculated using randomization date and date of death, or date of last follow-up for censored subjects. Time to death from any cause is defined as the time between randomization and death from any cause. All subjects will be followed until drop-out, death, or study closure. Drop-out may be due to withdrawal of consent from further data collection or lost to follow-up. Subjects who drop-out or are alive at study closure (or at the time of the interim analysis [Section 10.8]) will have their OS times censored at the time of last contact, as appropriate.

The analysis of OS will be performed using the ITT population for the interim and final analysis. The null hypothesis for testing the key secondary efficacy endpoint, time to death from any cause,

^{§§} As is consistent with medical practice in Japan, 1 unit RBC referenced in this protocol is equivalent to 2 units RBC in Japan.

is that the overall survival distributions for the two treatment groups are equivalent. Overall survival curves will be estimated using Kaplan-Meier (KM) methods and will be compared using a stratified log-rank test, stratifying by average baseline RBC transfusion requirement (≤ 4 units^{§§} versus > 4 units of RBC per 28 days), baseline platelet transfusion status (dependent or independent), country of enrollment (ie, Japan versus ROW) and ECOG performance status (0 to 1 versus 2). The p-value from the stratified log-rank test will be the confirmatory p-value. The p-value from the final analysis of the OS endpoint will be adjusted for the interim analysis in order to preserve the overall alpha level at 0.05 (see [Section 10.8](#) for further details regarding the interim analysis and methods for controlling the overall alpha level). Kaplan-Meier estimates for median OS as well as the 25th and 75th percentiles and associated two-sided 95% CIs will be summarized for each treatment group, unadjusted for the stratification variables. In addition, both the numerical difference and the 95% CI of the difference, in the median, 25th, and 75th percentiles between the two treatment groups will be presented for the un-stratified analysis. Plots of the KM survival curves will be presented for the two treatment groups, without adjustment for the stratification variables.

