12 DISCONTINUATIONS

The following events are considered sufficient reasons for discontinuing a subject from the investigational product and/or from the study:

- Lack of Efficacy
- Progressive Disease ([Table 3](#))
- Adverse event(s)
- Withdrawal of consent
- Death
- Lost to follow up
- Protocol violation

Although lack of efficacy or progressive disease is considered a sufficient reason for discontinuing a subject from protocol-prescribed therapy, the investigator should continue to treat the subject until the investigator considers protocol-prescribed therapy to be no longer beneficial to the subject, or the change of disease state renders the subject unacceptable for further treatment in the judgment of the investigator. The decision to discontinue a subject, which will not be delayed or refused by the sponsor, remains the responsibility of the treating physician. However, prior to discontinuing a subject, the investigator may contact the Medical Monitor and forward appropriate supporting documents for review and discussion.

The reason for discontinuation will be recorded in the CRF and in the source document for all randomized subjects, regardless of whether they are dosed or not.

Subjects discontinued from the investigational product will not be replaced.

All subjects discontinued from protocol-prescribed therapy for any reason should undergo Treatment Discontinuation procedures ([Section 6.13](#)), and will be followed for a period of 28 days following the last dose of IP or until the date of the last study visit, whichever period is longer as described in [Section 6.14](#).

All subjects discontinued from protocol-prescribed therapy for any reason will also be followed for survival, subsequent MDS therapies, progression to AML and second primary malignancy as described in [Section 6.14](#).

Table 3: Definitions of Progressive Disease for Clinical Decision on Discontinuing Subjects from the Investigational Product and/or from the Study

Category	Progression/Relapse ^{†††} Criteria
Progression in Bone Marrow	
For subjects with:
 
Less than 5% blasts at baseline: > 50% increase in blasts to > 5% blasts
 
5%-10% blasts at baseline: ≥ 50% increase to > 10% blasts
 
Note: A 2nd bone marrow sample should be collected within 4 weeks to confirm progression before discontinuing subjects from treatment.

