APPENDIX J EXTENSION PHASE

Once all 216 subjects enrolled have completed 12 months of double-blind treatment or have discontinued before reaching 12 months of double-blind treatment and Amendment 5 of the protocol is approved at the respective sites, and after study unblinding by Celgene, eligible subjects can enter the Extension Phase.

Subject Eligibility

At the Investigator's discretion and following confirmation of eligibility criteria below, subjects can enter the extension phase:

- Subjects who have signed the informed consent for the EP of the study;
- Subjects randomized to the oral azacitidine treatment arm and continuing in the Treatment Phase demonstrating clinical benefit as assessed by the Investigator are eligible to receive oral azacitidine in the EP;
- Subjects randomized into the placebo arm of the study will not receive oral azacitidine in the EP, but will be followed for survival in the EP;
- Subjects currently in the Follow-up Phase, after permanent study treatment discontinuation, will continue to be followed for survival in the EP;
- Subjects who do not meet any of the criteria for study discontinuation (see [Section 12](#)).

Treatment Assignment

Subjects will start the EP at the start of their next regularly scheduled dosing cycle for oral azacitidine and align Cycle 1 Day 1 with the Treatment Discontinuation visit, so they occur on the same day. The dose and schedule will follow the study treatment administration and schedule ([Section 8.2](#)).

Cycles should be repeated every 28 days. Subjects should be monitored locally for hematology and chemistry testing, pregnancy testing for FCBP and dose limiting toxicities before the dosing of the next cycle. Dosage delay or reduction as described below may be necessary.

Management of Toxicities and Dose Modifications

Subjects should be monitored for toxicity using the National Cancer Institute (NCI) Common Terminology Criteria for Adverse Events (CTCAE, Version 4.0), as a guide for the grading of severity. If a certain level of toxicity is observed and considered by the investigator to be at least possibly related to treatment, IP dosing may be interrupted, delayed or modified. In all cases, the reason for dose modification must be recorded in the subject's medical record. If the subject discontinues the protocol-prescribed therapy because of an AE, this event must be reported in accordance with the procedures outlined in [Section 12](#).

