6. SUBJECT DISPOSITION

All subjects screened/randomized will be included in these analyses.

The disposition of subjects will be summarized with counts and percentages. Summaries will include the number of subjects screened and randomized. For subjects randomized, subject disposition will be summarized for analysis population by treatment group and overall for:

- ITT Population
- mITT Population
- Safety Population

Reasons for excluding subjects from mITT population will be summarized and listed for each subject in the ITT population. A separate listing will be provided for subjects who were not randomized. A frequency table of enrollment by site and treatment will be provided.

The reasons for excluding subjects from mITT population are:

1. Did not have at least one post-baseline efficacy assessment;
2. Did not meet all inclusion/exclusion criteria;
3. Did not receive a minimum of one cycle of treatment.

The post-baseline efficacy assessments include any type of transfusions, local or central lab of Hgb and/or platelets count, disease status assessment (by investigator), IWG MDS Response assessment (by investigator), and assessment of bleeding events.

Subjects who have been dosed in Cycle 2 will be considered as receiving a minimum of one cycle of treatment. For subjects who did not have Cycle 2 treatment, they will be considered as receiving a minimum of one cycle of treatment if: 1) they have been dosed (actual dose) for at least 21 days if they were assigned to “21 days” dose; or 2) they have been dosed (actual dose) for at least 14 days if they were assigned to “14 days” dose. Days with missing (or zero) dose due to any reason will not be included in the “21 days” or “14 days”.

Number of subjects who are ongoing in treatment and number of subjects who are ongoing in follow-up will be tabulated. Reasons for study drug discontinuation as collected on the CRF will be summarized for all ITT subjects with the following categories:

- Adverse events
- Lack of efficacy
- Withdrew consent
- Death
- Lost to follow-up
- Protocol violation
- Progressive disease
- Sponsor Decision
- Other

Reasons for study discontinuation as collected on the CRF will be summarized for all randomized subjects with the following categories:

- Death
- Adverse Event
- Pregnancy
- Progressive Disease
- Lack of Efficacy
- Recovery
- Withdrew Consent
- Non-compliance with study drug
- Lost to follow-up
- Study terminated by sponsor

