- Transition to commercially available treatment
- Protocol Violation
- Other

A by-subject listing of subject's reason for discontinuation will be presented.

7. **PROTOCOL DEVIATIONS/VIOLATIONS**

The protocol deviations/violations will be identified and assessed by clinical research physician or designee following company standard operational procedure. The protocol deviations/violations will be summarized by treatment group for the ITT population.

A by-subject listing of subjects with protocol deviations/violations in the ITT population will be provided.

CELGENE PROPRIETARY INFORMATION

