10.2.1. Key Secondary Endpoint

Overall survival (OS), defined as the time from randomization to death from any cause, will be calculated using randomization date and date of death, or date of last follow-up for censored subjects. Time to death is defined as the time between randomization and death from any cause. All subjects will be followed until drop-out, death, or study closure. Drop-out may be due to withdrawal of consent from further data collection or lost to follow-up. Subjects who drop-out or are alive at study closure (or at the time of the interim analysis [Section 15.2]) will have their OS times censored at the date of last known alive, as appropriate.

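### Protocol Section 12, the SAP 6 exit categories and the Extension Phase eligibility rule do not separate stopping study drug from leaving the study, and so conflict with the overall survival follow-up rules

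*Protocol*

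**What the plan says.** Two groups of passages bear on this.

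**Passages that let a subject leave the study**

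- Protocol Section 12: "The following events are considered sufficient reasons for discontinuing a subject from the investigational product and/or from the study". One list follows: lack of efficacy, progressive disease, adverse events, consent withdrawal, death, loss to follow-up and protocol violation. The Table 3 title uses the same *and/or* construction for progressive disease.
- SAP 6 has one list of reasons for stopping study drug and a second for leaving the study: "Reasons for study discontinuation as collected on the CRF will be summarized for all randomized subjects with the following categories". The second includes adverse event, progressive disease, lack of efficacy, non-compliance with study drug, protocol violation and "Transition to commercially available treatment".
- The EP eligibility list (Protocol Summary and Appendix J) ends with "Subjects who do not meet any of the criteria for study discontinuation" and points to Section 12. Protocol 4.1.4 makes survival follow-up in the EP subject to EP eligibility.

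**Passages that keep every subject under survival follow-up**

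- Protocol Section 12, after the list: "All subjects discontinued from protocol-prescribed therapy for any reason will also be followed for survival".
- Protocol 6.14 runs that follow-up "until death, lost to follow-up, or withdrawal of consent for further data collection". Protocol 4.1.3 and SAP 4.1.3 give the same end points.
- Protocol 10.6.2.1, on OS: "Drop-out may be due to withdrawal of consent from further data collection or lost to follow-up". SAP 10.2.1 repeats this, and says that subjects who drop out, or are alive at closure or at the interim, "will have their OS times censored at the date of last known alive".

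**The concern.** OS is the key secondary endpoint and sits in the formal testing sequence. Its analysis treats censoring as unrelated to prognosis. A subject who leaves the study at progression, for an adverse event or on moving to another drug leaves when the risk of death has probably changed. If nobody learns later whether that subject died, the record is cut at the last date known alive. Two things are then at stake: deaths that the final analysis counts on, and, if exits depend on prognosis, the log-rank test and hazard ratio.

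The two groups of passages give a site different instructions. Neither OS section says how to treat a subject recorded as leaving the study for progression, an adverse event or a protocol violation, because neither recognises that such a subject exists.

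**Working it through.** **1. The passages side by side**

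| Reason | Section 12: may leave the study? | SAP 6 study-exit category? | Ends survival follow-up (6.14)? | Named OS drop-out (10.6.2.1, SAP 10.2.1)? |
|---|---|---|---|---|
| Progressive disease | Yes | Yes | No | No |
| Lack of efficacy | Yes | Yes | No | No |
| Adverse event | Yes | Yes | No | No |
| Protocol violation | Yes | Yes | No | No |
| Move to commercial treatment | Not listed | Yes | No | No |
| Consent withdrawal | Yes | Yes | Yes, if from further data collection | Yes, if from further data collection |
| Loss to follow-up | Yes | Yes | Yes | Yes |

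The first four rows conflict outright. The fifth conflicts only between SAP 6 and the OS rules.

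**2. The EP bullet.** A subject who stopped drug for progression has met a Section 12 criterion. Taken literally, the last eligibility bullet keeps that subject out of the EP, and Protocol 4.1.4 then removes EP survival follow-up. A neighbouring bullet says that subjects already off treatment continue to be followed for survival in the EP. The two cannot both apply to that subject.

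**3. The plan's own OS figure.** Inputs (Protocol 10.3): 205 deaths, hazard ratio (HR) 0.70, 1:1 allocation, two-sided alpha 0.05. By the Schoenfeld formula, power = Φ(√(d/4) × |ln HR| − 1.96) = Φ(√51.25 × 0.3567 − 1.96) = Φ(0.593) = 72.4%. The stated 72% reproduces.

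**4. Slack in deaths.** 205/216 = 94.9%, and 216 − 205 = 11. Once more than 11 subjects end without a recorded death, 205 cannot be reached, however long follow-up runs. With exponential medians of 18 and 25.7 months, 56 months of uniform accrual, a 134-month study and no drop-out, expected deaths are 207.0, which is 2 above the target.

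**5. What extra loss would cost (illustration).** Hazards are λ = ln 2/18 and ln 2/25.7 per month. Drop-out is a competing exponential hazard η, the same in both arms and unrelated to prognosis. For follow-up f, P(death observed) = λ/(λ+η) × (1 − exp(−(λ+η)f)), averaged over f from 78 to 134 months. Power is for a single analysis at HR 0.70.

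| Share lost | Expected deaths at 134 months | Power |
|---|---|---|
| 5% (plan's assumption) | 198 | 70.8% |
| 10% | 188 | 68.7% |
| 20% | 169 | 63.9% |
| 30% | 149 | 58.6% |

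**6. Direction of bias (illustration).** Two illness-death simulations were run, with progression and death hazards assumed, not taken from the documents. Both have a true OS HR of 0.78.

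- *Model A:* placebo median 18 months; progression hazard 0.035 per month on placebo and 60% lower on active; death hazard triples after progression; exit at progression. If 25% of placebo and 10% of active progressors exit, HR reads 0.82 with about 195 deaths, against 213 with no exit. At 50% and 25% it reads 0.87 to 0.88 with 174 deaths. Equal shares of 25% or 50% give 0.80 or 0.83. Reversing the first case (10% placebo, 25% active) gives 0.76.
- *Model B:* progression hazards 0.06 and 0.035; death hazard 0.012 before and 0.06 after progression; exit one month after progression, equal shares. At 10%, 25% and 50%, HR moves from 0.781 to 0.775, 0.766 and 0.757, and deaths fall from 212 to 197, 173 and 134. With no treatment effect, HR stays at about 1.00.

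Equal exit shares push HR up in A and down in B. Deaths fall in every exit case where they were counted.

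**The case against.** The strongest reply is that Section 12 largely answers itself. Just after the list it describes lack of efficacy and progressive disease as grounds for stopping protocol-prescribed therapy, and the marrow note in Table 3 speaks of discontinuing treatment. It then requires survival follow-up whatever the reason, and Protocol 6.14 asks investigators to make every effort to learn survival status before declaring a subject lost. SAP 6 is a descriptive table of reasons taken from the CRF. It also lists pregnancy and recovery, which suggests generic categories, and it authorises nobody to end follow-up. The neighbouring EP bullets plainly intend that treated and untreated subjects alike be followed for survival.

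Most of this stands as evidence of intent. It does not remove the conflict. The clarifying sentence covers only lack of efficacy and progressive disease, not adverse events or protocol violation. SAP 6 shows that study exit for these reasons can be recorded separately from stopping drug. The EP bullet still contradicts its neighbour.

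A reader might also infer more than the documents support:

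- *That OS is informatively censored.* No passage censors the confirmatory OS analysis at progression, lack of efficacy or a change of drug. Censoring at subsequent MDS therapy is a sensitivity analysis only (Protocol 10.6.2.1, SAP 10.2.1).
- *That Section 12 allows exit for a move to commercial treatment.* That reason appears only in SAP 6.
- *That the simulated hazard ratios measure bias in this trial.* Their progression, post-progression and exit inputs are assumed, and no exit counts are given.

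**Conclusion.** The inconsistency is real and should be corrected. Section 12, the Table 3 title and the EP bullet state or imply that a subject may leave the study for reasons that the follow-up and OS sections do not accept, and SAP 6 provides categories to record such exits. Read literally, these passages could censor OS informatively and lose deaths.

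What can be sized is the margin: 11 subjects of 216, or about 2 expected deaths at the planned 134 months on the planning assumptions with no drop-out. The amount of bias and its direction cannot be stated. Both depend on how many subjects exit, in which arm and with what prognosis, and the documents are silent on all three.

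The point bears on the final OS analysis. The interim belongs to the primary analysis, whose study report, with a data cut-off of 25 January 2019, was final by 4 February 2020. Separately, Appendix J under Amendment 6.0 limits EP survival follow-up to 35 ± 7 days after treatment discontinuation, while Protocol 10.6 continues it until 205 deaths. That is a different conflict, not counted here, but it also limits how many deaths the final analysis can capture.

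**What to change.** - Split Section 12 into (a) reasons to stop investigational product, which is the existing list unchanged, and (b) reasons to end study follow-up: death, withdrawal of consent to further data collection, loss to follow-up and study closure. This takes no position on when treatment should stop.
- Delete the words that extend list (a) to leaving the study, both in Section 12 and in the Table 3 title.
- Reword the EP eligibility bullet in the Protocol Summary and Appendix J so that the Section 12 drug-stopping criteria limit continued treatment only, not survival follow-up. Align Protocol 4.1.4.
- Keep the SAP 6 categories as collected. Cutting them to list (b) would hide the exits of interest. Tabulate by arm the subjects recorded as leaving the study for any reason outside list (b).
- Where consent allows, retrieve vital status for those subjects and count their deaths in the final OS analysis.

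The cost is protocol and SAP wording and a few vital-status queries, with no new visits. The table by arm will also show whether the problem occurred at all.

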13 EMERGENCY PROCEDURES

13.1 Emergency Contact

In emergency situations, the Investigator should contact the responsible Clinical Research Physician/Medical Monitor or designee by telephone at the number(s) listed on the Emergency Contact Information page of the protocol (after title page).

In the unlikely event that the Clinical Research Physician/Medical Monitor or designee cannot be reached, please contact the global Emergency Call Center by telephone at the number listed on the Emergency Contact Information page of the protocol (after title page). This global Emergency Call Center is available 24 hours a day and 7 days a week. The representatives are responsible for obtaining your call-back information and contacting the on call Celgene/Clinical Research Organization (CRO) Medical Monitor, who will then contact you promptly.

Note: The back-up 24 hour global emergency contact call center should only be used if you are not able to reach the Clinical Research Physician(s) or Medical Monitor or designee for emergency calls.

13.2 Emergency Identification of Investigational Products

The blind must not be broken during the course of the study unless, in the opinion of the investigator, it is absolutely necessary to safely treat the subject. If it is medically imperative to know what IP the subject is receiving, IP should be temporarily discontinued ([Section 8.9](#)).

The investigator may contact the Medical Monitor prior to breaking the blind to discuss unblinding, mainly in the interest of the subject. However, the decision to break the blind in emergency situations remains the responsibility of the treating physician, which will not be delayed or refused by the sponsor.

The investigator should ensure that the code is broken only in accordance with the protocol. The investigator should promptly notify the Medical Monitor of the emergency unblinding and the reason for breaking the blind, which should be clearly documented by the investigator in the subject's source documentation.

Emergency unblinding should only be performed by the investigator through the IRT system by using an emergency unblinding personal identification number (PIN), and the investigator should access the IRT system for unblinded dose information.

